8.1.2 Randomization and Blinding

The NeuroNEXT IWR system will be used to randomize subjects according to the scheme predefined by the DCC and will also serve to inform the unblinded study pharmacist of the treatment assignment. Subjects will be randomized to either 3K3A-APC or placebo. There are 22 groups of four subjects planned, but fewer may be enrolled should the study meet either of the early stopping criteria. Additionally, if two consecutive cohorts are in the DLT review period, subjects will be

assigned to placebo. The additional placebo subjects will be closely monitored and their enrollment may be discontinued should the number enrolled exceed what was planned for the study. Subjects will not be considered part of the ITT cohort until they receive any amount of 3K3A-APC or placebo. For example, 'Early Responders,' subjects whose symptoms resolve between initial randomization and initiation of IMP infusion such that they are no longer eligible (repeat NIHSS <5), will be removed from the study and replaced. Any given subject who receives only one dose of study drug and does not experience a DLT will not be included in the CRM calculation (i.e. two or more doses will need to be administered to be included).

8.2 Outcomes

8.2.1 Primary Outcome (Including Definition)

The primary objective of the study is to evaluate the safety of multiple ascending intravenous (IV) doses of 3K3A-APC following tPA administration or mechanical thrombectomy or both in subjects who have experienced moderate to severe acute ischemic stroke. Safety will be assessed by defining dose-limiting toxicities (DLTs), which will be graded using the National Cancer Institute (NCI) Common Terminology Criteria for Adverse Events (CTCAE), Version 4.03.

DLTs will be assessed from the first dose to 48 hours following the last dose of 3K3A-APC (unless specified below), and will be defined as any of the following AEs that have an attribution of "related" to study treatment (possibly, probably and definitely):

- An activated partial thromboplastin time (aPTT) that reaches 2x the upper limit of normal (ULN) at 1 hour post-dose. The ULN range is defined locally by the site laboratory.
- Symptomatic intracranial hemorrhage (SICH) defined as blood present on CT or MRI brain images that is associated with clinical worsening that meets the definition of neuroworsening (4 or more point increase in NIHSS; see section 9.4.1.3 for definition) and in the opinion of the Investigator represents a clinically significant change that can be attributed to the hemorrhage. Subarachnoid hemorrhage that occurs in subjects who receive mechanical thrombectomy will NOT be considered a DLT, and instead will be evaluated in an exploratory analysis upon study completion.
- Laboratory findings that meet all of the following three components (Hy's Law):
 - ≥ 3x ULN of alanine aminotransferase (ALT) or aspartate aminotransferase (AST)
 - Serum total bilirubin (TBL) >2x ULN, without initial findings of cholestasis [serum alkaline phosphatase (ALP) activity >2x ULN)
 - And, no other reason can be found to explain the combination of increased aminotransferase (AT) enzymes and TBL, such as viral hepatitis A, B, or C, preexisting or acute liver disease, or another drug capable of causing the observed injury.
- Any other bleeding event classified as serious by the Investigator, or any bleeding that required the administration of more than 2 units of packed red cells over any two consecutive days.

- Any Grade 3 laboratory value that, in the opinion of the Investigator, is related to study treatment. Refer to CTCAE v4.03 sections relevant to laboratory investigations.
- Any adverse event that in the opinion of the Investigator is related to study treatment and leads to cessation of further dosing.

NOTE: All suspected DLTs will be reviewed by a Safety Review Committee, and those reported DLTs that are considered possibly related to study drug but definitely related to another event will not be considered DLTs upon final adjudication. An example of such an event would be an elevated aPTT following dose 1 in a subject who undergoes mechanical thrombectomy during which heparin is administered; the elevated aPTT can be attributed to the heparin and therefore should NOT be considered a DLT in this isolated instance. Another example would be the occurrence of hypofibrinogenemia in a subject who receives tPA. Low fibrinogen levels can be attributed to tPA, and there is a documented rate of occurrence of 11% in subjects receiving tPA⁸. Furthermore, 3K3A-APC does not cause a reduction in the level of fibrinogen in plasma and therefore this finding should NOT be considered a DLT.

- Incidence of subarachnoid hemorrhage in subjects who receive mechanical thrombectomy
- 7-day National Institutes of Health Stroke Scale (NIHSS) scores
- 90-day modified Rankin Scale (mRS)
- 90-day Barthel Index (BI)
- Infarct volume at 90 days (MRI, or CT if unable to obtain MRI)
- Pre-Dose 1, Day 14 and Day 30 anti-drug antibody samples

8.3 Sample Size and Accrual

8.3.1 Primary Outcome

In order to assess the adequacy of the sample size, we conducted a simulation study to examine the ability of the study to identify the MTD under a range of assumed scenarios. The scenarios under consideration are summarized below in Table 4. The scenarios describe the full range of possibilities:

- Scenario 1 considers the case where all doses are safe (i.e., true toxicity probability is below the target threshold for each dose.
- Scenarios 2-5 consider the case where the true target toxicity level of 10% occurs at each successive dose level under consideration.
- Scenario 6 considers the case where no dose level is safe (i.e., true toxicity probably is above the target threshold for all doses.

Scenario	Description		Dose	Level		
		120	240	360	540	
1	MTD = Dose 4	0.05	0.05	0.05	0.05	
2	MTD = Dose 4	0.05	0.05	0.07	0.10	
3	MTD = Dose 3	0.05	0.07	0.10	0.15	
4	MTD = Dose 2	0.05	0.10	0.15	0.20	
5	MTD = Dose 1	0.10	0.15	0.20	0.25	
6	No MTD	0.15	0.20	0.25	0.30	

Table 4. Assumed True Toxicity Probabilities for Simulation Scenarios

The results of the simulation study are summarized in table 5, and contrasted to the results from a pure 3+3 design (which was proposed in the original version of the protocol). Below, we provide a short summary of the findings from the simulation study:

- In scenario 1, both CRM approaches and the 3+3 method select the highest dose with high probability.
- In scenarios 2-5, both CRM approaches generally do a better job at selecting the "correct" dose as the MTD. The 3+3 method does slightly better at selecting the highest dose when

it is the MTD (scenario 2). However, this comes at a cost of "overshooting" the MTD when the true MTD occurs at a lower dose – as high as 88% under scenario 5.

 In scenario 6, the CRM approaches correctly conclude that no dose satisfies the criteria of MTD over half of the time, whereas the 3+3 has a small probability of declaring no MTD and seems to select any of the four doses in a near uniform manner.

	D	0		sults of Simu				%True	
Scenario	Dose	9	6 Recommen	aea	# Su	# Subjects Allocated			
	Level						Toxicity		
		0014	0014	0.0	0.0014	0014	0.0	CRM	
		CRM		3+3	CRM		3+3		
1	None	0%	1%	1%					
	120	2%	2%	2%	8.1	11.5	3.5	5%	
	240	3%	4%	2%	5.3	8.9	3.4	5%	
	360	4%	5%	3%	5.4	8.0	3.6	5%	
	540	91%	88%	91%	42.2	32.6	45.2	5%	
2	None	1%	1%	1%					
	120	4%	4%	2%	9.3	12.4	3.4	5%	
	240	9%	9%	2%	8.3	10.8	3.4	5%	
	360	19%	19%	10%	10.4	11.4	4.4	7%	
	540	68%	67%	86%	36.8	29.7	33.8	10%	
3	None	1%	1%	1%					
	120	10%	10%	2%	13.8	15.7	3.5	5%	
	240	25%	25%	4%	14.0	14.9	3.6	7%	
	360	32%	31%	19%	14.2	13.9	5.0	10%	
	540	32%	33%	74%	23.6	20.9	23.1	15%	
4	None	1%	2%	1%					
	120	27%	26%	2%	22.0	22.5	3.5	5%	
	240	42%	42%	8%	19.1	19.3	4.1	10%	
	360	21%	21%	29%	12.4	12.6	5.6	15%	
	540	9%	10%	59%	12.1	11.1	15.5	20%	
5	None	21%	20%	3%					
_	120	54%	54%	9%	37.4	36.9	4.0	10%	
	240	20%	20%	16%	12.5	13.9	4.4	15%	
	360	5%	5%	32%	6.1	6.4	5.2	20%	
	540	1%	1%	41%	4.8	3.8	9.4	25%	
6	None	61%	61%	6%			-		
-	120	34%	34%	19%	39.4	39.0	4.5	15%	
	240	4%	4%	22%	6.2	7.7	4.5	20%	
	360	1%	1%	29%	2.8	2.7	4.4	25%	
	540	0%	0%	24%	1.9	1.3	5.2	30%	

Table 5. Results of Simulation Study

In summary, both modified CRM approaches generally have better performance with respect to successfully recommending the correct dose as the MTD (based on prior assumptions), and are well suited to achieve the goals of this study. The modified CRM being used here performs no better than the more traditional approach at identifying the true MTD when it occurs at one of the intermediate doses. Clearly, better accuracy could be achieved by increasing the sample size for the study. However, when weighed against the costs of a larger study, the proposed sample size provides the right balance with respect to selecting the correct dose across all scenarios, and ZZ-3K3A-201 Version 8.1 Final

Version date 7-Oct-2016

considering the probabilities of both 'undershooting' and 'overshooting' the assumed true MTD. Some efficiency is sacrificed by using the lagged version of the modified CRM. However, this minor loss of efficiency is completely offset by the operational advantages of requiring fewer "extra placebo subjects" be enrolled.

8.3.2 Secondary Outcome (Bleed Rates)

We also assessed the power of the study to evaluate bleed rates between all treated subjects (collapsed across doses) versus placebo subjects. Previous experience suggests that the MRIdetected bleed rate for tPA-treated subjects should be approximately 30%-40%⁵⁶⁻⁶². Furthermore, it is expected from pre-clinical studies that treatment with APC could lead to a rather dramatic decrease in bleed rates for 3K3A-treated subjects^{31,44,63}. Pre-clinical data suggest that 3K3A-APC could reduce bleeding seen after IV tPA or after mechanical thrombectomy^{44,63}. Thus, it is expected that the study could observe a difference between the groups as substantial as a reduction from a 40% bleed rate among placebo subjects to a lack of observed bleeding in the treated group. However, to assess power over a range of conditions, we computed power for all combinations of the following conditions:

- Placebo group bleed rates of 20%, 30%, & 40%
- 3K3A-APC treated group bleed rates of 0.5%, 5%, & 10%
- Overall sample sizes of 48 (36 treated / 12 control) and 88 (66 treated / 22 control) in
 order to assess power under the scenario where the trial proceeds to the end and under
 the scenario where the study stops early for lack of observing any toxicity at the highest
 dose

Table 6 provides a summary of these power calculations. In general, we find:

- If the original assumptions are correct: We would have very high power (>90%) in either scenario
- If the original assumption regarding the placebo rate is correct, but the treated rate is a bit higher:

We would have very good power (>85%) if the study proceeds to the end. We would have lower, but a still acceptable level of power (>64%) if the study stops due to a lack of observed toxicity after 12 cohorts.

• If the original assumption regarding the treatment rate is correct, but the placebo rate is a bit lower:

We would have decent power (>66%) in either scenario, and very good power (>84%) in the scenario where the study proceeds to the end.

• If both assumptions are wrong (placebo rate lower, treatment rate higher): There is lower power overall, but still reasonable power in a number of settings (such as 30% placebo rate versus 10% treated rate)

In conclusion, it appears that the study has adequate power to detect differences in bleeding of interest, even if our assumptions are slightly optimistic. We believe that this sufficiently supports the adequacy of the comparison of bleeding rates.

Assumed Bleed Rate	Assumed Bleed Rate in Placebo Group								
in Treated Group	20)%	30)%	40%				
	N = 48	N = 88	N = 48	N = 88	N = 48	N = 88			
0.5%	66%	84%	82%	95%	92%	99%			
5%	39%	56%	63%	83%	80%	96%			
10%	18%	26%	41%	61%	64%	85%			

Table 6. Power for Comparing Bleed Rates (Assumes Chi-Square Test, Significance Level = 0.05, and 75% of Subjects Assigned to Treatment)

8.4 Data Monitoring

All aspects of the study will be monitored by qualified individuals designated by the sponsor. Monitoring will be conducted according to Good Clinical Practice and applicable government regulations. The Investigator agrees to provide monitors access to the clinical supplies, dispensing and storage areas, and to the clinical files of the study subjects, and, if requested, agrees to assist the monitors. The site will provide the monitor adequate working space and full access to the medical record. If the site uses an electronic medical record, the monitor will be provided a temporary password and access to one patient chart, or, the site coordinator will be available throughout the monitoring visit to provide access. The site PI will be available for an exit visit with the monitor.

Safety monitoring will include careful assessment and appropriate reporting of adverse events. Medical monitoring will include contemporaneous assessment of serious adverse events.

The monitoring of subject safety and data quality will follow the NINDS Guidelines for Data and Safety Monitoring in Clinical Trials. A Data and Safety Monitoring Board (DSMB) appointed by the NIH/NINDS will meet at approximately six-month intervals (or as determined by the NINDS) to review partially unblinded study data provided by the study statistician. This committee will monitor rates of adverse events and endpoints in the trial and will monitor the performance of the trial. The frequency and format of DSMB meetings, reports, and guidelines for interim analysis will be agreed upon prior to study subject enrollment during the first meeting of the DSMB with the representatives of the DCC. The DSMB will review the data seen by the SRC during their deliberations of dose escalation steps.

The Protocol PI will appoint an Independent Medical Monitor (IMM) to review all adverse events in a blinded real-time fashion in order to monitor for AEs that could meet the definition of a DLT. Should a DLT be reported or suspected, the IMM will notify the SRC, which will be convened to review the AE(s). In addition, the IMM will review all events that meet the regulatory definition of a Serious Adverse Event, upon receipt of notification via the Electronic Data Capture (EDC).

An adverse event (AE) is any untoward medical occurrence associated with the use of a drug in humans whether or not considered drug related. FDA, Office of Human Research Protection (OHRP), and NeuroNEXT CIRB requirements for reporting AEs will be followed. Subjects who receive investigational treatment will be monitored for AEs from the time they sign consent until 7 days for AEs and 30 days for SAEs following permanent discontinuation of study drug. At that point, all ongoing AEs will be followed to resolution, or until Day 90, but no new AEs will be recorded. The IMM/DSMB will review cumulative AEs; the frequency of this review will be determined by the IMM/DSMB in conjunction with the Protocol PI.

Each Clinical Study Site Principal Investigator (CSS PI) and research team (co-Investigators, research nurse, clinical trial coordinator) are responsible for identifying and reporting AEs. The CSS PI is responsible for determining the relationship of the event to the study drug/study procedures. Aggregate reports blinded by treatment group, detailed by severity, attribution (expected or unexpected), and relationship to the study drug/study procedures, will be available from the DCC for review by the IMM. A separate report detailing protocol compliance will also be available monthly from the DCC for review by the Protocol PI, who will provide feedback to individual sites as needed. The Protocol Steering Committee (PSC) will advise the Protocol PI as to whether the protocol or informed consent document requires revision based on these reports.

8.5 Data Analyses

8.5.1 Primary Objective

Determine Maximum Tolerated Dose: The MTD will be selected using the rules specified above for the implementation of the CRM model. The MTD will be defined as the dose that would be chosen from the CRM model at the final step. Additional safety assessments will compare the groups on the basis of all AEs, changes in laboratory and vital signs values, and results of physical examinations. AEs will be classified with regard to seriousness, severity, duration, and relatedness of the event. AE data will be listed individually and will be descriptively summarized by body system, preferred terms within a body system, and treatment dose.

8.5.2 Secondary Objectives

Secondary Outcome #1 (PK Parameters): Based upon analysis of PK data from the Phase I study, a one-compartment IV infusion model will be used and will be parameterized in terms of the primary parameters clearance (CL) and volume of distribution (V). Secondary parameters will include C_{max} , AUC_{0-inf}, and $t_{1/2}$ – and will be calculated from the primary parameters. The actual times of the beginning and end of all 5 infusions and each blood sampling time relative to the first dose will be used in the modeling. All modeling will be done using WinNonlin.

Secondary Outcome #2 (Bleed Rates): To assess tPA/mechanical thrombectomy-related bleed rates across the two groups, all treated subjects (regardless of dose) will be compared to all placebo subjects using a Pearson chi-square test. An additional analysis will compare the bleed rates among placebo subjects and subjects treated at each dose level (assuming a sufficient number of subjects were treated at that level).

Exploratory Outcomes: (Stroke Outcome and Immunogenicity Data): To inform the design of any future Phase III trial, the following exploratory outcomes will be compared at the end of the study. Unless explicitly stated otherwise, the comparisons will be conducted first comparing all treated subjects (regardless of dose) versus all placebo subjects, and then comparing all subjects receiving the dose selected as the MTD versus all placebo subjects.

• The mean bleeding (hemorrhage and microbleeds) volume at Day 30 will be compared using a linear regression model. Median and categorical volumes (based upon quartiles) will be compared.

- Rates of subarachnoid hemorrhage in subjects who receive mechanical thrombectomy will be compared; all mechanical thrombectomy 3K3A-APC-treated subjects (regardless of dose) will be compared to all placebo subjects using a Pearson chi-square test.
- The 7-day NIHSS mean scores will be compared using a Kruskal-Wallis test.
- The change from Baseline NIHSS to 7-day NIHSS will be compared using a linear regression model, with baseline NIHSS score as a covariate.
- The 90-day mRS will be compared using a Pearson chi-square test.
- The mean infarct volume at 90 days (MRI, or CT if unable to obtain MRI) will be compared using a linear regression model. Median and categorical infarct volumes (based upon quartiles) will be compared.
- The 90-day BI will be compared using a Kruskal-Wallis test.
- The relationship between the 7-day NIHSS score and the 90-day mRS will be examined using a linear regression model. The degree of fit and the R-square will be determined, and the model will be used to assess the potential for using the 7-day outcome in subsequent studies.
- The tendency of the drug to induce an immunogenic response in patients will be assessed.

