1.3 Exploratory Objectives

- To evaluate the effect of 3K3A-APC on the volume of tPA/mechanical thrombectomyrelated bleeding (hemorrhage and microbleeds) in the brain as determined by MRI at Day 30.
- To evaluate the effect of 3K3A-APC on incidence of subarachnoid hemorrhage in subjects who receive mechanical thrombectomy.
- To collect the 7-day National Institutes of Health Stroke Scale (NIHSS) scores as a predictor for 90-day modified Rankin Scale (mRS).
- To collect the 90-day mRS
- To collect the 90-day Barthel Index (BI)
- To collect infarct volume at 90 days (MRI, or CT if unable to obtain MRI)
- To assess the immunogenic potential of 3K3A-APC

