4 SELECTION AND ENROLLMENT OF SUBJECTS

4.1 Inclusion Criteria

- 1. Age 18 to 90 years, inclusive
- 2. Acute ischemic stroke defined as focal, neurological deficit(s), secondary to a presumed vascular occlusive event
- 3. Able to receive IV tPA per local standard of care, OR, begin mechanical thrombectomy per local standard of care.
- 4. National Institutes of Health Stroke Scale (NIHSS) score ≥ 5 at time of randomization
- 5. Signed informed consent by subject or authorized representative
- 6. Agreement to use effective birth control throughout the study (i.e., Day 90):
 - a. Males barrier method of contraception plus a spermicide
 - b. Females of childbearing potential (i.e., not surgically sterile or post-menopausal defined as age > 51 years without menses for ≥ 2 years) hormonal contraception or barrier method of contraception plus a spermicide
- 7. Willing (subject and/or caretaker) to commit to follow-up assessments
- 8. Mechanical thrombectomy subjects only: onset (last-seen-well) time to arterial puncture time < 6 hours

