2. PRIMARY ENDPOINT

The primary objective of the study is to evaluate the safety of multiple ascending intravenous (IV) doses of 3K3A-APC following tPA administration in subjects who have experienced moderate to severe acute hemispheric ischemic stroke. Safety will be assessed by defining dose limiting toxicities (DLTs), which will be graded using the National Cancer Institute (NCI) Common Terminology Criteria for Adverse Events (CTCAE), Version 4.03.

DLTs will be assessed from the first dose to 48 hours following the last dose of study treatment (unless specified below), and defined as any of the following AEs that have an attribution of “related” to study treatment (possibly, probably and definitely):

- An activated partial thromboplastin time (aPTT) that reaches 2x the upper limit of normal (ULN) at 1 hour post-dose. The ULN range is defined locally by the site laboratory.
- Symptomatic intracranial hemorrhage (SICH) defined as blood present on CT or MRI brain image that is associated with clinical worsening that meets the definition of neuroworsening (4 or more point increase on the NIHSS; see section 10.3 for definition) *and* in the opinion of the investigator represents a clinically significant change that can be attributed to the hemorrhage. Subarachnoid hemorrhage that occurs in subjects who receive mechanical thrombectomy will NOT be considered a DLT, and instead will be evaluated in an exploratory analysis upon study completion.
- Findings that meet all of the following three components (Hy’s Law):
 - $\geq 3x$ ULN of alanine aminotransferase (ALT) or aspartate aminotransferase (AST)
 - Serum total bilirubin (TBL) $> 2x$ ULN, without initial findings of cholestasis [serum alkaline phosphatase (ALP) activity $> 2x$ ULN]
 - And, no other reason can be found to explain the combination of increased aminotransferase (AT) enzymes and TBL, such as viral hepatitis A, B, or C, pre-existing or acute liver disease, or another drug capable of causing the observed injury.
- Any other bleeding event classified as serious by the Investigator, or any bleeding that required the administration of more than 2 units of packed red cells over any two consecutive days.
- Any Grade 3 laboratory value that, in the opinion of the investigator, is related to study treatment.

- Any adverse event that, in the opinion of the investigator, is related to study treatment and leads to cessation of further dosing.

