8.3 Exploratory Outcomes

A number of additional exploratory analyses are also planned, but will not be included as part of the FSR. Unless explicitly stated otherwise, the comparisons will be conducted first comparing all treated subjects (regardless of dose) versus all placebo subjects, and then comparing each dose individually. These exploratory analyses include, but are not limited to the analyses described below.

- This study will include additional bleeding outcome data of interest. While the sample size is likely too small to observe meaningful treatment effects, the data allow confirmation that outcomes in this trial resemble previously published trials. Corresponding, the following exploratory analyses will be considered:
 - Evaluating the effect of 3K3A-APC on the volume of tPA/mechanical thrombectomy related hemorrhage in the brain as determined by MRI at Day 30
 - Evaluating the effect of 3K3A-APC on the incidence of subarachnoid hemorrhage in subjects who receive mechanical thrombectomy
 - Evaluating the effect of 3K3A-APC on the incidence of hemorrhage at Day 7.
- To inform the design of any future phase II/III trial, the study will also include outcome data typically collected in all stroke trials, as well as sample collection to assess the immunogenic potential of 3K3A-APC. Correspondingly, additional exploratory analyses will include comparisons across groups for:
 - Day 7 National Institute of Health Stroke Scale (NIHSS) Scores
 - Change from Baseline NIHSS to Day 7 NIHSS
 - Day 90 Modified Rankin Scale (mRS)
 - Infarct Volume at 90 Days (MRI, or CT if unable to obtain MRI):
 - Day 90 Barthel Index (BI) Scores
 - The relationship between the 7-day NIHSS score and the 90-day mRS will be examined using a linear regression model. The degree of fit and the R-square will be determined, and the model will be used to assess the potential for using the 7-day outcome in subsequent studies.
 - Pre-Dose 1, Day 14, and Day 30 Anti-Drug Antibody Samples: The tendency of the drug to induce an immunogenic response in patients will be assessed.

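### Protocol 8.5.2 contradicts itself on who the placebo comparators are for subarachnoid hemorrhage, and SAP 8.3 does not settle it; the literal reading leans toward false harm

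*Protocol*

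**What the plan says.** Protocol 8.5.2 handles SAH in one sentence with two halves. The first half sets the population: "Rates of subarachnoid hemorrhage in subjects who receive mechanical thrombectomy will be compared". The second half names the groups and the test: "all mechanical thrombectomy 3K3A-APC-treated subjects (regardless of dose) will be compared to all placebo subjects using a Pearson chi-square test". The thrombectomy limit is repeated for the drug group and left off the placebo group.

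The other descriptions agree with the first half:

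- Protocol 1.3, objective: "To evaluate the effect of 3K3A-APC on incidence of subarachnoid hemorrhage in subjects who receive mechanical thrombectomy"
- Protocol 8.2.2, outcome list: "Incidence of subarachnoid hemorrhage in subjects who receive mechanical thrombectomy"
- SAP 8.3, planned exploratory analysis: "Evaluating the effect of 3K3A-APC on the incidence of subarachnoid hemorrhage in subjects who receive mechanical thrombectomy"

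SAP 8.3 gives no test and no comparator specific to SAH. Its default for exploratory outcomes is "Unless explicitly stated otherwise, the comparisons will be conducted first comparing all treated subjects (regardless of dose) versus all placebo subjects".

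Two further statements matter. Protocol 4.1 admits subjects treated by either route: "Able to receive IV tPA per local standard of care, OR, begin mechanical thrombectomy per local standard of care". SAP 2, like the corresponding protocol sections, takes the event out of the primary endpoint: "Subarachnoid hemorrhage that occurs in subjects who receive mechanical thrombectomy will NOT be considered a DLT". It defers the event to an exploratory analysis.

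**The concern.** Someone programming the analysis from the clause that names the groups would set thrombectomy subjects on drug against every placebo subject, including those who had tPA alone. Drug and procedure would then be confounded. The plan itself treats SAH after thrombectomy as a separate matter, which suggests that the procedure carries its own SAH risk. If it does, the subjects without thrombectomy pull the placebo rate down, and a drug with no effect appears to raise the SAH rate.

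This is the only comparison dedicated to an event that was removed from the DLT definition, and Protocol 8.5.2 says the exploratory results are meant to inform a future Phase III trial. A spurious intracranial bleeding signal would be an unhelpful thing to carry forward. The bias runs toward showing harm, so it would not hide a real one.

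**Working it through.** **No figure to reproduce.** Neither document states an SAH rate, a thrombectomy share, a power or an alpha for this comparison. SAP 6 states 0.05 for the key secondary objectives; two-sided 0.05 is assumed here.

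**Inputs from the documents.** 66 treated and 22 placebo in the 88 cohort subjects (Protocol 8.3.2). About 115 subjects in total with the extra placebo subjects (Protocol 8.1.1), so about 115 − 66 = 49 placebo.

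**Assumed inputs, not in the documents.** Thrombectomy share f of 40–60% in both arms; SAH rate s of 3–20% with thrombectomy; SAH rate u of 1% without; no drug effect.

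**Step 1: expected rates on the literal reading.** The drug rate is s. The placebo rate is a mixture, f·s + (1 − f)·u. For 66/49 with f = 50% and s = 10%, there are 33 thrombectomy subjects on drug and, among 49 on placebo, 24 with thrombectomy and 25 without:

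- Placebo rate = (24 × 0.10 + 25 × 0.01)/49 = 2.65/49 = 5.4%
- Rate ratio with no drug effect = 10/5.4 = 1.85

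If u were 0, the ratio would be about 1/f, or 2.0 at f = 50%. If u equalled s, there would be no dilution and no bias.

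**Step 2: how often the test rejects.** Exact binomial enumeration of the uncorrected Pearson chi-square (critical value 3.841). Literal means thrombectomy drug subjects against all placebo; matched means thrombectomy subjects in both arms. Entries are total rejection rates.

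| f | s | Literal, 66/49 | Matched, 66/49 | Literal, 66/22 | Matched, 66/22 |
|---|---|---|---|---|---|
| 40% | 3% | 7.7% | 1.0% | 0.1% | 1.4% |
| 40% | 10% | 16.8% | 4.6% | 4.4% | 2.9% |
| 40% | 20% | 28.5% | 4.8% | 16.4% | 3.9% |
| 50% | 3% | 3.0% | 1.4% | 0.4% | 1.7% |
| 50% | 10% | 12.3% | 5.2% | 3.6% | 2.9% |
| 50% | 15% | 19.2% | 5.6% | 7.6% | 3.4% |
| 50% | 20% | 26.1% | 5.4% | 11.3% | 4.1% |
| 60% | 3% | 1.2% | 2.0% | 0.4% | 1.9% |
| 60% | 10% | 8.6% | 5.4% | 3.2% | 3.0% |
| 60% | 20% | 16.7% | 4.4% | 9.7% | 4.8% |

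Wherever the literal test is inflated, nearly all of its rejections are in the direction of harm (at 66/49, f = 50%, s = 10%: 12.2 of the 12.3 points). The matched test's harm-direction rate in that cell is 2.2%.

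**Step 3: what drives the size.** The inflation grows with the SAH rate and with the extra placebo subjects, and shrinks as the thrombectomy share rises. With 22 placebo subjects and SAH of 3–5%, the literal test rejects in under 1% of trials.

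**The case against.** The strongest reply is that the sentence should be read whole. Its first half fixes the population for both arms, and all placebo subjects then means all of them within that population. The objective, the outcome list and SAP 8.3 say the same. The SAP (version 2.0, December 2017) is also later than Protocol 8.1 (October 2016) and does not repeat the one-sided clause; its all-treated versus all-placebo default, applied inside the thrombectomy population, gives the matched comparison.

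Much of this stands. A reader might infer that the plan has decided to include placebo subjects without thrombectomy. The documents do not support that: no section says so, and the matched comparison was probably intended. What remains is that the only clause naming both the groups and the test carries the limit for one arm and drops it for the other, and that SAP 8.3 does not name the placebo group that would settle the matter.

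A reader might also infer that this is the only planned test that could reach SAH. It is not. SAP 10.8 compares treatment-emergent and treatment-related AEs and SAEs between drug and placebo by system organ class, and by preferred term where a class differs. Those comparisons use the full arms and do not have this mismatch, although they are not restricted to thrombectomy and the preferred-term step is conditional.

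Finally, the consequences are small. SAP 8.3 keeps these analyses out of the Final Study Report, Protocol 8.2.2 concedes that the sample is too small for meaningful treatment effects, and nothing here touches the CRM, the MTD or a stopping rule. That stands and sets the severity.

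**Conclusion.** The point holds as an internal contradiction in Protocol 8.5.2 that SAP 8.3 leaves unresolved; it does not establish that the mismatched comparison was chosen. Followed literally, the clause answers a different question from the stated objective and leans toward false harm, provided SAH is more common with thrombectomy than without.

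Under the assumed inputs, the literal test rejects a true null about 1–28% of the time with 66/49 and 0.1–16% with 66/22, against at most about 6% when the arms are matched. The width of those ranges reflects how little the documents say about the SAH rate and the thrombectomy share; at the low end there is no inflation at all. Severity is minor.

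**What to change.** In Protocol 8.5.2, add the words *who received mechanical thrombectomy* after the mention of the placebo subjects, so that both arms carry the same limit. In SAP 8.3, name that same comparator and the test.

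As a secondary improvement, allow Fisher's exact test when expected counts are small, as SAP 8.2 already does for hemorrhage rates. With matched arms, f = 50% and s = 10%, only 24 × 0.10 = 2.4 placebo events are expected with 49 placebo subjects, and 11 × 0.10 = 1.1 with 22.

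The cost is one clause in each document. Design, conduct, data collection and sample size do not change.
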